13.4.1.2. Serious Adverse Event Reporting (Eagle V1.2 and PD G 506 A)

Aes considered by the participant's treating *surgeon* to be a SAE as defined in Section 13.1.2 (regardless of relatedness) will be reported via the SAE Report Form within 24 hours of awareness to:

spmd – safety strategies for health, Inc. [name]

Email: [contact]

[contact]

13.4.1.3. Other Events to be reported within the same timelines as SAEs (PD G 506 A only)

13.4.1.3.1. Overdose, Abuse, Misuse, Medication Errors, Occupational Exposure and other uses outside what is foreseen in the protocol

Definition overdose: Administration of a quantity of an investigational medicinal product given per administration or cumulatively which is above the maximum recommended dose according to the protocol dosing instructions. Clinical judgement should always be applied.

Definition abuse: Persistent or sporadic, intentional excessive use of an investigational medicinal product, which is accompanied by harmful physical or psychological effects.

Definition misuse: Situations where the investigational medicinal product is intentionally and inappropriately used not in accordance with the protocol dosing instructions.

Definition medication error: Unintended failure in the drug treatment process that leads to or has the potential to lead to harm to the patient.

Definition occupational exposure: The exposure to an investigational medicinal product, as a result of one's professional or non-professional occupation.

SBI-CIP 20-002 Rev: v1.8 A prospective multi-center clinical study evaluating the use of PD G 506 A and the Eagle V1.2 Imaging System for the visualization of carcinoma during breast conserving surgery	Page: 88 of 157
---	-----------------

Drug overdose, drug abuse, drug misuse, medication errors, occupational exposure and other uses outside what is foreseen in the protocol should be reported in the same format (i.e. on SAE Report Form) and within the same timelines as a SAE, even if they may not result in an adverse outcome.

13.4.1.3.2. Reporting of Pregnancy

If a participant becomes aware that they are pregnant following consenting to participate and prior to receiving the investigational drug, their participation in the study will be terminated immediately. If a participant becomes aware that they are pregnant following administration of the investigational drug but prior to completing the study, they will complete the study according to the protocol. The PI will be responsible for reporting such an event within 24h of becoming aware that the participant is pregnant to:

spmd – safety strategies for health, Inc. [name]

Email: [contact]

[contact]

via the SAE Report Form.

The PI will request written permission to follow-up with the participant to pregnancy outcome. See **Appendix 5** for more detailed information.

Spmd on behalf of SBI ALApharma Canada Inc. will identify missing information and requests for follow-up will be sent directly to the Investigator. Spmd will inquire follow-up information in regular intervals form the investigators until all queries are resolved or not further information can be reasonably expected.

All responses to queries and supply of additional information by the investigator should follow the same reporting route and timelines as the initial report.

13.4.1.4. Investigational Product Complaints

Investigators are responsible for reporting any investigation drug and investigational device deficiency encountered. Reporting of such deficiencies are required even when they do not directly or indirectly contribute or potentially could have contributed to a reportable AE. Reporting of deficiencies that meet the criteria of an (S)AE must be reported according to **Sections 13.4.1** and 13.4.2). The PI will be responsible for reporting all other deficiencies in a timely manner, and no later than 15 calendar days after becoming aware of the deficiency to:

spmd – safety strategies for health, Inc.

SBI-CIP 20-002 Rev: v1.8 A prospective multi-center clinical study evaluating the use of PD G 506 A and the Eagle V1.2 Imaging System for the visualization of carcinoma during breast conserving surgery	Page: 89 of 157
---	-----------------

[name]

Email: [contact]

[contact]

[figure not shown]
spmd will report all non-AE deficiencies to SBI ALApharma Canada Inc., who will investigate the deficiency and take corrective and preventative actions if warranted in accordance with GMP to protect the safety of participants, users, and other persons.

	BI-CIP	Rev:	A prospective multi-center clinical study evaluating the use of PD G	
1 -	20-002	v1.8	506 A and the Eagle V1.2 Imaging System for the visualization of	Page: 90 of 157
Ľ	20-002	V1.6	carcinoma during breast conserving surgery	

13.4.2. Regulatory Reporting of Adverse Events to Competent Authorities (Health Canada & FDA) and Ethic Committees (REBs & IRBs)

13.4.2.1. Summary of Regulatory Reporting Obligations

13.4.2.1.1. Canada

Q1: Is the AE serious?

A: No \rightarrow document in eCRF \rightarrow no further actions required.

B: Yes \rightarrow document on SAE Report Form & send to spmd within 24h \rightarrow document in eCRF \rightarrow continue with Q2

Q2: Is the event related to the Investigational Device (Eagle V1.2)?

[figure not shown]
A: No \rightarrow no further actions required

B: Yes → fill out "Medical Device Problem Report Form for Health Care Professionals" and send to Health Canada within 72h

Figure 13.1: (S)AE Reporting Algorithm for Canada (LT= life threatening)

SBI-CIP 20-002 Rev: v1.8 A prospective multi-center clinical study evaluating the use of PD G 506 A and the Eagle V1.2 Imaging System for the visualization of carcinoma during breast conserving surgery	Page: 91 of 157
---	-----------------

13.4.2.1.2. USA

Q2: Is the event related to the Investigational Device (Eagle V1.2)?

A: No → no further actions required

B: Yes \rightarrow continue with Q3

Q3: Is the event expected for the Investigational Device (Eagle V1.2)?

A: No, event is unexpected → report event as UADE to IRB within 10 working days

B: Yes, event is expected → not further actions

Figure 13.2: (S)AE Reporting Algorithm for USA (LT= life-threatening; bd= business days)

13.4.2.2. PD G 506 A: SUSAR Reporting

spmd, on behalf of SBI ALApharma Canada Inc. will be responsible for reporting all serious and unexpected adverse events, which are judged as having a reasonable suspected causal relationship to the Investigation Drug PD G 506 A (Suspected Unexpected Serious Adverse Reaction – SUSAR) to the Food and Drug Administration and Health Canada.

SBI-CIP 20-002 Rev: v1.8 A prospective multi-center clinical study evaluating the use of PD G 506 A and the Eagle V1.2 Imaging System for the visualization of carcinoma during breast conserving surgery	Page: 92 of 157
---	-----------------

Spmd, on behalf of SBI ALApharma Canada Inc. will be responsible for providing the CIOMS I Form (Canada) MedWatch Form (USA) for all SUSARs to the PI for reporting to their REB/IRB of Record according to local requirements.

The PI will report:

- All fatal/ life-threatening SUSARs within 7 calendar days; and
- All other SUSARs within 15 calendar days;

to their REB/IRB on Record according to local requirements.

13.4.2.3. Eagle V1.2 Imaging System: SAR/ UADE Reporting

spmd, on behalf of SBI ALApharma Canada Inc. will be responsible for reporting all serious adverse events, which are judged as having a reasonable suspected causal relationship to the Investigational Device Eagle V1.2 Imaging System (Serious Adverse Reaction – SAR) to Health Canada.

Spmd, on behalf of SBI ALApharma Canada Inc. will be responsible for reporting all serious and unexpected adverse events, which are judged as having a reasonable suspected causal relationship to the Investigational Device Eagle V1.2 Imaging System (Unanticipated Adverse Device Effect – UADE) to the Food and Drug Administration.

The Canadian PI will report:

- All SARs within 72 hours to Health Canada using the "Medical Device Problem Report Form for Health Care Professionals"; and
- All fatal/ life-threatening UPs/UADEs within 7 calendar days to their REB on Record according to local requirements
- All other UPs/UADEs within 15 calendar days to their REB on Record according to local requirements.

Spmd, on behalf of SBI ALApharma Canada Inc. will be responsible for providing the CIOMS I Form (Canada) for all UADEs to the PI for reporting to their REB of Record according to local requirements.

The US PI will report:

• All UADEs within 10 business days to their IRB of Record according to local requirements.

13.4.2.4. Unanticipated Problem (UP) Reporting

UPs that do not meet the criteria of an AE (e.g. events that place the participant or others at a greater risk of physical or psychological harm than was previously anticipated, or have implications for the conduct of the study or the integrity of research data) will be reported by the PI to their REB/IRB of Record as well as spmd at:

SBI-CIP 20-002 Rev: v1.8 A prospective multi-center clinical study evaluating the use of PD G 506 A and the Eagle V1.2 Imaging System for the visualization of carcinoma during breast conserving surgery	Page: 93 of 157
---	-----------------

spmd – safety strategies for health, Inc.

[name]

Email: [contact]

[contact]

The following are examples of non-AE Ups which would require reporting the REB/IRB:

- An increase in the rate of occurrence of an expected SAE that is judged by the PI or sponsor to be clinically important
- A major safety finding from a newly completed animal study that indicated significant risk to human participants or the specific population being studied
- Breaches of privacy or confidentiality

13.5. Study Pausing Rules

Administration of investigational drug within the study will be paused when three grade 3 AEs determined to be "probably" or "definitely" related (as determined by the Investigator) to the investigational drug or three grade 3 AEs determined to be "probably" or "definitely" related to the investigational device are reported in the clinical database. SBI ALApharma Canada Inc. and spmd will receive an automatic notification from the clinical database indicating the 3rd such AE has been recorded. Spmd will inform investigators within 1 business day of the third grade 3 "possibly" or "definitely" related event being reported, and administration of study drug and enrolment of new study patients will be stopped. In parallel, spmd will inform the DSMB and CATO-SMS that the study has been paused. Within 1 business day of being notified that the study has been paused, CATO-SMS will provide the DSMB and spmd with AE listing reports. The DSMB will provide recommendations to SBI ALApharma Canada Inc. and spmd for proceeding with the study, including a recommendation for future suspension of enrolment and study drug administration if additional drug- or device-related ("probably" or "definitely") AEs are reported. Spmd will inform the Investigators on the decision of the DSMB. SBI ALApharma Canada Inc. will inform the appropriate regulatory authorities of the temporary pause and the disposition of the study.

Administration of the investigational drug within the study will also be suspended if any drug- or device-related ("possibly", "probably" and "definitely"; as determined by the Investigator or Sponsor) SAE is reported to spmd. Spmd will notify SBI ALApharma Canada Inc. and investigators within 1 business day of this SAE being reported. Enrolment of new study patients and administration of study drug will be stopped. In parallel, spmd will inform the DSMB and will provide the DSMB with the SAE report. The DSMB will provide recommendations for proceeding with the study to SBI ALApharma Canada Inc. and spmd. Spmd will inform the Investigators on the decision of the DSMB. ALApharma Canada Inc. will inform the appropriate regulatory authorities of the temporary pause and the disposition of the study.

carcinoma during breast conserving surgery
--

Part A is an open-label training phase of the study to refine workflow and provide training. SBI ALApharma Canada Inc., the Study Steering Committee and the DSMB will be closely monitoring the workflow issues as patients are enrolled and will determine when this process has been optimized. It is anticipated that no more than 75 subjects will be required for Part A. If necessary, enrollment may be temporarily suspended after completion of the first 30 patients in Part A prior to initiating Part B so that sample size estimation can be confirmed and any other necessary amendments can be incorporated into the protocol.

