13.2.2. Clarification of the difference in meaning between "severe" and "serious"

The term "severe" is often used to describe the intensity (severity) of a specific event (as in mild, moderate, or severe myocardial infarction); the event itself, however, may be of relatively minor medical significance (such as severe headache).

This is not the same as "serious", which is based on the outcome or action criteria usually associated with events that pose a threat to life or functioning.

Seriousness (not severity) serves as a guide for defining regulatory reporting obligations.

Spmd, on behalf of SBI ALApharma Canada Inc., will be responsible for reviewing all AE reports regarding the PI's determination of the severity of the event.

carcinoma during breast conserving surgery	1	Rev: v1.8	A prospective multi-center clinical study evaluating the use of PD G 506 A and the Eagle V1.2 Imaging System for the visualization of carcinoma during breast conserving surgery	Page: 83 of 157
--	---	--------------	--	-----------------

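### Section 13.5: the sentence that notifies investigators and stops enrolment says 'possibly' or 'definitely' related, where the three-event trigger says 'probably' or 'definitely'

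*Combined protocol and SAP*

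**What the plan says.** Protocol Section 13.5 contains two pausing rules. The first counts events and runs as a sequence within one paragraph:

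- **Trigger, drug.** Dosing is paused at "three grade 3 AEs determined to be 'probably' or 'definitely' related (as determined by the Investigator) to the investigational drug".
- **Trigger, device.** The same applies at "three grade 3 AEs determined to be 'probably' or 'definitely' related to the investigational device are reported in the clinical database".
- **Database notice.** The sponsor and the pharmacovigilance vendor receive an "automatic notification from the clinical database indicating the 3rd such AE has been recorded".
- **Action.** The vendor has one business day to inform investigators, and the clock starts at the "third grade 3 'possibly' or 'definitely' related event being reported". The same sentence then sets the consequence for the trial: "administration of study drug and enrolment of new study patients will be stopped". The DSMB and the contract research organisation are told in parallel.
- **DSMB advice.** The DSMB may recommend future suspension "if additional drug- or device-related ('probably' or 'definitely') AEs are reported".

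The second rule concerns serious events. Administration is "suspended if any drug- or device-related ('possibly', 'probably' and 'definitely'; as determined by the Investigator or Sponsor) SAE is reported to spmd", and enrolment stops as well.

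Section 13.2.3 defines definitely, probably and possibly related as three separate grades. It notes that a possibly related event may later be upgraded to either of the higher two.

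**The concern.** The action sentence uses a different causality threshold from the trigger that it is meant to carry out. It names the lowest of the three related grades and the highest, and skips the one between. That is not a coherent threshold in its own right.

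The sentence has consequences of its own. The trigger sentence pauses drug administration only. Within the count rule, only the action sentence sets the one-business-day notice to investigators and stops enrolment. Read literally, three probably related grade 3 events would pause dosing without starting the notice or the enrolment stop. Three possibly related ones would stop dosing and enrolment although the trigger had not been met.

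The rule on serious events does not remove the problem. Section 13.2.2 says of severity: "This is not the same as 'serious', which is based on the outcome or action criteria". A grade 3 event can therefore be non-serious and fall under the count rule alone.

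There is a smaller gap in the same paragraph. The count rule says grade 3, whereas the safety endpoints in Section 7.4 and the safety analysis in Section 15.8 cover grades 3 to 5. A related grade 4 event judged non-serious is literally left out of the count.

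**Working it through.** The plan gives no figure to reproduce here. The check compares the wording sentence by sentence.

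**Relatedness grades named in Section 13.5**

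| Sentence | Possibly | Probably | Definitely |
|---|---|---|---|
| Trigger, drug | no | yes | yes |
| Trigger, device | no | yes | yes |
| Database notice | refers back to the trigger | | |
| Action (investigators told, enrolment stopped) | **yes** | **no** | yes |
| DSMB advice on further events | no | yes | yes |
| Separate rule for serious events | yes | yes | yes |

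Within the count rule the pair probably/definitely appears three times and possibly/definitely once. The DSMB sentence repeats only the relatedness words, without the grade or the count of three. Where the plan does mean to count possibly related events, in the rule for serious events, it lists all three grades. Changing the one word makes all four explicit mentions in the count rule agree.

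**How often the two sentences differ when read literally**

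Take three grade 3 events attributed to the same product, each rated possibly (S), probably (P) or definitely (D) related. The number of unordered combinations is C(3 + 3 − 1, 3) = C(5, 3) = 10.

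- The trigger is met if every rating is P or D: PPP, PPD, PDD, DDD, which is 4.
- The action sentence is met if every rating is S or D: SSS, SSD, SDD, DDD, which is 4.
- Both are met by DDD only: 1.
- Trigger only: 4 − 1 = 3.
- Action sentence only: 4 − 1 = 3.
- Neither: 10 − 1 − 3 − 3 = 3 (SSP, SPP, SPD).

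The sentences disagree on 3 + 3 = 6 of 10 combinations. The combinations are not equally likely, so this describes the wording and says nothing about how often the conflict would arise. The restriction to one product comes from the trigger; the action sentence names no product.

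**The grade wording**

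Grade 5 is death, which is always serious under Section 13.1.2. For events outside the CTCAE list, Section 13.2.1 defines grade 4 as life-threatening, which is also a seriousness criterion. Any single related serious event already suspends the study. What remains uncounted is a related grade 4 event on the CTCAE list that is judged non-serious.

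**The case against.** The strongest reply is that the paragraph reads as one sequence and no informed reader would be misled. The database notice is tied to the trigger's threshold. 'The third' event in the action sentence most naturally means the one just notified, and the DSMB is told that the study has been paused. Nor does the plan describe any notice that would go out for three possibly related events, so an enrolment stop on those alone has no stated mechanism. Exposure is also limited on any reading: the drug is a single oral dose, the trigger pauses dosing by itself, and any related serious event, including a possibly related one, stops dosing and enrolment separately.

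This is right about intent and about the practical effect, and it is why the point is minor. It does not make the sentence correct. No other text in the plan overrides it, and several parties must act on it: the sponsor, the pharmacovigilance vendor, the contract research organisation, the DSMB and the sites.

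A second reply is that a pausing rule and a descriptive safety summary need not share a grade cut-off. The summaries are also labelled WHO grade, whereas events are graded by CTCAE. That is fair, and the comparison alone would not show an error. The case for 'grade 3 or higher' is that a count of grade 3 events should not pass over a more severe one.

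**Conclusion.** The concern holds as a minor internal inconsistency. The sentence in Section 13.5 that sets the notice to investigators and the enrolment stop states a different causality threshold from its own trigger. The word is almost certainly a slip for 'probably'. That rests on the rest of the paragraph, on the full listing of grades in the rule for serious events, and on the gap in the literal threshold; the plan does not itself confirm which word was meant. The literal conflict covers 6 of 10 rating combinations. No event rate or patient harm is claimed, and the risk is confined to someone applying the sentence as written to non-serious grade 3 events. The grade wording is a separate and narrower gap, limited to related, non-serious grade 4 events.

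**What to change.** In the Section 13.5 sentence on informing investigators, replace 'possibly' with 'probably'. In the same paragraph, write 'grade 3 or higher' in the drug trigger, the device trigger and the notice sentence. Leave the separate rule for serious events unchanged, since its inclusion of possibly related events is explicit. The change is a few words in one paragraph, with no effect on sample size, the efficacy analysis or the rule for serious events. It can go into the next amendment or a clarification letter to sites and vendors.

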13.6. Safety Oversight

Safety oversight will be under the direction of the DSMB composed of individuals with the appropriate expertise, such as but not limited to:

- Medical Oncology, Solid Tumor
- Surgical Oncology
- Radiation Oncology
- Clinical Research Nursing
- Biostatistics

The DSMB will meet at least semi-annually to assess safety data. The DSMB will operate under the rules of an approved charter that will be written and reviewed at the organizational meeting of the DSMB. Each data element that the DSMB needs to assess will be clearly defined at the 1st DSMB meeting. The DSMB will provide its input, in the form of recommendations directly to SBI ALApharma Canada Inc. and site PIs.

14. Clinical Monitoring

Clinical site monitoring is conducted to ensure that the rights and well-being of human subjects are protected, that the reported trial data are accurate, complete, and verifiable, and that the conduct of the trial is in compliance with the currently approved protocol/amendment(s), with GCP, and with applicable regulatory requirement(s).

The study monitor, in accordance with the sponsor's requirements, will ensure that the study is conducted and documented properly by carrying out the activities outlined in International Council for Harmonisation E6, Section 5.18.4 and as detailed in the study Monitoring Plan.

Types of monitoring will include:

- On-site and/or monitoring
- Centralized monitoring, including:
 - o targeted data verification
 - o confirmation of completion of eCRFs
 - o query resolution
 - o eligibility criteria review
 - o adverse event and concomitant medication review
 - o screening/enrolment data

SBI-CIP 20-002 Rev: v1.8 A prospective multi-center clinical study evaluating the use of PD G 506 A and the Eagle V1.2 Imaging System for the visualization of carcinoma during breast conserving surgery Page: 95 of 19	5 7
---	------------

- o review of anonymized FL imaging data for the purposes of identifying sites requiring re-training
- statistical monitoring to identify missing or invalid data and unusual data patterns which may indicate additional on-site monitoring and/or additional training is required

Each clinical site will perform internal quality management of study conduct, data collection, documentation and completion. Independent audits may be performed as required by the sponsor.

15. Statistical Considerations

